Imagery and Relaxation Training and IV Habituation Day. On LAB DAY 1, subjects will arrive at the lab at 11 AM on the day of the first laboratory session and an indwelling intravenous (IV) catheter will be inserted in the subject's arm so that subjects can habituate to the stress of an IV insertion. We have found that this period of adaptation is critical for stable baseline measurements on testing days. No blood will be drawn during this training period. After insertion of IV catheter, the subject will be provided with relaxation training followed by general imagery and physiological response training, as described in the imagery training procedures manual (Lang, Levin, Miller, & Kozak, 1983). The imagery training involves subjects' visualizing some commonplace scenes as they are presented to them. The scenes are neutral and non-emotional in content, such as reading a popular magazine. Following the imagery, the subject is asked questions about the visualization and given pointers regarding the process of imagining the scene. The subject also imagines scenes that are non-emotional but physically arousing in nature, such as doing sit-ups in gym class. With these scenes subjects are asked whether they notice any changes in their physiological response, such as change in heart rate or change in breathing. Once again, pointers with regard to imagining the situation "as if" they were really present in the situation are presented. This session takes approximately one hour and was developed to ensure that all subjects are trained on the method of generating an image and maintaining it for 2-3 minutes. At the end of training, the subject will be given lunch and prepared for the first laboratory session. .

Laboratory Sessions. In week 2 of the study PREG/PLA administration and hence DAY 1, 2 and 3 of the laboratory portion of the study, subjects will be brought into the research testing rooms of the Yale Stress Center (YSC) at 2:00 PM. The laboratory sessions will only be conducted if the subject has a breath alcohol level of 0, otherwise the session will be rescheduled. The subject will then be prepared for physiological assessments. An indwelling intravenous (IV) catheter will be inserted by the research nurse specialist in the antecubital region of the subject's non-preferred arm for blood sampling. Blood samples will be obtained periodically for assessment of neuroactive steroids, ACTH, cortisol, prolactin, NE and EPI levels. A blood pressure cuff will be placed on the subject's preferred arm to monitor blood pressure (BP) periodically. On-line assessment of physiological measures will be obtained at specified time periods during the laboratory sessions. Self-reports of emotional state, anxiety and alcohol craving will also be assessed periodically.

After preparation of assessments and a 40 minute adaptation period, two blood draws before imagery will be conducted (BASELINE). After the second blood draw, a 5-minute baseline period will follow to assess continuous pulse rate and BP assessments. Following the baseline period, instructions for conducting imagery will be provided. The order and content of the imagery condition will not be revealed to the subject or to the research staff conducting the

sessions. In the imagery task the subjects will be asked to imagine the situation being described vividly, 'as if it were happening right now", until asked to stop. The imagery script will be played to the subject over headphones and the subject will be required to imagine the situation for 5 minutes. A tape recording for each subject's script will be developed prior to the testing situation and recorded by the same person for each subject. Immediately following imagery, a blood draw will be conducted (IMAGERY). Thereafter, four recovery blood draws will be conducted at 15 minute intervals (RECOVERY). Timeline for assessments is detailed in Table 1.

TABLE 1: Schedule for Laboratory Sessions

LAB DAY 1 11AM: Imagery and Relaxation Training and IV Habituation session (1 hour)

LAB DAY 1, 2 and 3: LABORATORY (IMAGERY) TESTING SESSIONS

2:00 PM	Set-up for plasma (IV insert) measures; physiological Setup - HR, BP, Finger Temp, SCL.
2:10 PM	Stabilization and Adaptation period, BP reading
2:40 PM (-20)	Initial Blood Draw (25 cc, includes 10 cc for RNA isolation), craving/DES ratings,
	physiological measurements
2:50 (-10)	BASELINE Period; on-line physiological recordings; baseline cognitive tasks
2:55 (-5)	Baseline blood draws; craving/DES ratings, BP assessments
3:00	IMAGE Period (Stress/Alcohol Cues/Neutral); physiological recordings
3:10 (0)	Post-Image blood draw (25 cc, includes 10 cc for RNA isolation); craving/DES ratings;
3:15 (+5)	RECOVERY Period; 5-min physiological recordings; craving/DES ratings; cognitive tasks;
3:25 (+15)	Recovery 1: Blood draws, craving/DES ratings; physiological assessments
3:45 (+25)	; Craving/DES and Physiological monitoring
3:55 (+45)	Recovery 2: Blood draws, craving/DES ratings; physiological assessments
4:10 (+60)	Recovery 3: Blood draws (25 cc, includes 10 cc for RNA isolation), craving/DES ratings; physiological assessments
4:25 (+75)	Recovery 4: Blood draws, craving/DES ratings; physiological assessments
4:40(+90)	Recovery 5: Blood draws, craving/DES ratings; physiological assessments
4:55 (+105)	Relaxation tape; assess physiological levels & subjective state for return to baseline
5:00 PM	BAC assessment continues until under .02. Once BAC reaches <.02, the subject is debriefed and leaves the session.

15 ml of whole blood will be collected at each time point (total of 360 mls over 3 days).

Relaxation instructions will be provided to ameliorate any residual effects of imagining personal stressful and drug cue situations. Subjects will then be free to leave the testing room. Relaxation instructions have been found to be effective in reducing drug cue-induced craving (Margolin, Avants, & Kosten, 1994; Sinha et al., 1999a) in the laboratory and we will use

these instructions to reduce any residual alcohol craving. At the end of the third laboratory session, subject will meet with the PI or her designee for a motivational interviewing session to consider the harmful effects of alcohol on their body and to increase their motivation to initiate recovery. To facilitate and support subjects' commitment to treatment, all subjects will meet with a clinician once/weekly for treatment counseling for the 4-week study period.

Laboratory Assessments.

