3. **Research Plan:** Summarize the study design and research procedures using non-technical language that can be readily understood by someone outside the discipline. **Be sure to distinguish between standard of care vs. research procedures when applicable, and include any flowcharts of visits specifying their individual times and lengths.** Describe the setting in which the research will take place.

1. Study Design and Overview

Ninety treatment seeking men and women with AUD will be recruited to participate in and complete this preliminary study. Participants will be recruited through flyers and advertisements in local newspapers and from community substance abuse treatment facilities. Subjects will participate in an initial screening and intake session to obtain informed consent, followed by physical examination and blood work to determine eligibility. Eligible

participants will be randomly assigned to 2 doses of PREG (300/500 mg/day) vs placebo (PLA) treatment (N=30/group) over 8 weeks. In week 2, AUD patients will participate in a 3day human laboratory study where they will be exposed to three experimental sessions of stress, alcohol cue and neutral-relaxing imagery on separate days (Fox et al.,2007; 2009; Sinha et al., 2008; 2009; 2011). Throughout the study, participants will come twice-weekly to the Yale Stress Center to receive medication, counseling and provide urine samples for UTOX. Women will be enrolled during the mid-luteal phase of the menstrual cycle so that laboratory sessions will be scheduled during the early to mid-follicular phase of the cycle when endogenous sex hormone levels are low prior to ovulation. PREG doses and matching placebo will be obtained by Yale IDS for compounding and dosing to 300mg and 500mg of PREG or PLA. Participants will self-administer study medication on a twice-daily dosing schedule throughout entire study.

Subjects will begin with full respective dose of medication immediately without a titration period, as previous studies with similar doses of pregnenolone up to 500 mg/day at b.i.d. dosing to be well tolerated and with no side effects (Marx et. al., 2009; Marx et al., 2014; Brown et al., 2014; Sripada et al., 2013).

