Imagery Script Development Session: In a session prior to the laboratory sessions, scripts for the guided imagery induction will be developed. The *stress imagery script* will be based on subjects' description of a recent personal stressful event that they had experienced as "most stressful". "Most stressful" is determined by having the subjects rate the perceived stress experienced by them on a 10-point Likert scale where "1=not at all stressful" and "10=the most stress they felt recently in their life". Only situations rated as 8 or above on this scale are accepted as appropriate for script development. Stressful situations that involved drug-related stimuli, such as being arrested for possession of drugs or being caught in a police chase, are not allowed. Examples of acceptable stressful situations include breakup with significant other, a verbal argument with a significant other or family member or unemployment-related stress, such as being fired or laid off from work. As stressful situations often occur in the context of alcohol use, these situations are thought to be associated with drug use and therefore elicit alcohol craving.

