The *drug-related script* will be developed by having subjects identify a recent situation that included drug-related stimuli and served as a trigger for subsequent alcohol use (e.g. buying crack, being at a bar and watching others use drugs/get high; getting together with drug using buddies). Drug-related situations that occurred in the context of negative affect or psychological distress will not be allowed, i.e., going to a bar after a marital conflict, or feeling depressed and calling a drug using buddy. A *neutral-relaxing script* will be developed from the subjects' commonly experienced neutral-relaxing situations. Neutral-relaxing events that involve drug cues will not be allowed. A 'script' or description of each situation will be developed using Scene Development Questionnaires which obtain specific stimulus and response details, including specific physical and interpersonal context details, verbal/cognitive attributions regarding the people involved, and physiological and bodily sensations experienced for the situation being described. The three scripts for each subject will then be recorded on an audio-tape for guided imagery in the laboratory sessions. The order of stress, neutral and drug cue scripts will be assigned randomly, and counterbalanced across subjects. Detailed procedures are outlined in the Imagery Development Procedures Manual (Sinha, 2001b).

Manipulation Check for Script Development: All three scripts will be rated on a Likert scale from 1 to 10 on a standard rating form (Independent Rating Scale) by two objective independent raters for stressful and emotional content. If a script scores below a rating of 8 for stressful content on a five-point rating scale the subject will be asked to develop a new script at

the next appointment prior to the laboratory sessions. These procedures ensure that the stress and drug cue scripts of all subjects are equated in intensity and content. It further ensures that differences in stress reactivity are not due to differences in intensity and emotional content of the stressor. The procedures for development of imagery scripts, rating of scripts for content and physiological activation are similar to those used by Miller et al. (Miller et al., 1987) and have been successfully used in our previous work on emotions (Sinha et al., 1992; Sinha & Parsons, 1996) and on stress reactivity with alcohol dependent individuals (Sinha et al., 1999a).

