During each laboratory session, about 120mL of whole blood will be drawn to measure stress hormone levels that may change during the session, totaling 360 mL for all three laboratory sessions. The amount of blood drawn over three laboratory sessions is equal to a little over onehalf the blood obtained during a regular blood donation. In addition, 32 mL of whole blood will be drawn on the first day of laboratory session to look at genetic markers, and 10mL of whole blood will be drawn during the physical exam/admission procedure to assess eligibility and look at molecular adaptations during the study. Lastly, 15 mL of whole blood will also be drawn each at weeks 2, 5 and 7 to measure pregnenolone levels. These levels will allow staff to ensure subjects are taking medication as prescribed. Thus, a total amount of 432 mL of whole blood will be drawn throughout the entire study. People who are in good health are not usually affected by this kind of blood loss. However, to be safe, subjects will be warned against donating blood for at least eight weeks after completing this study and 5 weeks beforehand.

III) Laboratory Sessions:

(1). Intravenous (IV) Catheter: When an IV is started, there is some risk that subjects may develop a bruise or bleeding where the vein is punctured. If this occurs, appropriate treatment will be instituted immediately. On extremely rare occasions, fainting, blood clot or infection may occur.

(2). The Imagery Procedures: The imagery method involves reliving a personal stressful event and can be somewhat anxiety provoking at the time of the task. Our previous experience has shown that once the task is over, there is very little anxiety that carries over, thus posing minimal risk. The alcohol cue imagery involves reliving a personal experience involving alcohol-related stimuli associated with alcohol use. While subjects may feel aroused by the alcohol cue imagery, relaxation procedures have been shown to be successful in reducing the physiological arousal associated with cue exposure and stressful imagery. It is likely that moderate craving for alcohol may occur due to subjects' imagining and reliving stressful events and drug cue related events. It is also possible that craving for alcohol may linger even after the task. In order to ensure that subjects are not put at increased risk for alcohol consumption after the laboratory sessions, the following safeguards will be taken:

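### The script-building rule defines the cue condition by drug-related stimuli and bars only drug cues from the stress and neutral scripts, although the trial tests alcohol-cue craving

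*Combined protocol and SAP*

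**What the plan says.** The rules for building the three imagery scripts are in Section V.3, Imagery Script Development Session.

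- **Cue script.** Participants are asked to "identify a recent situation that included drug-related stimuli and served as a trigger for subsequent alcohol use". The examples are "buying crack, being at a bar and watching others use drugs/get high; getting together with drug using buddies".
- **Stress script.** "Stressful situations that involved drug-related stimuli, such as being arrested for possession of drugs or being caught in a police chase, are not allowed". The same paragraph adds: "As stressful situations often occur in the context of alcohol use, these situations are thought to be associated with drug use".
- **Neutral script.** "Neutral-relaxing events that involve drug cues will not be allowed".
- **Check.** Under Manipulation Check for Script Development, two independent raters score all three scripts for how stressful and how emotional they are. Alcohol or drug content is not rated.

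Elsewhere the condition is described in terms of alcohol. The Study Design and Overview (Section V.3) plans "three experimental sessions of stress, alcohol cue and neutral-relaxing imagery on separate days". Table 1 labels the imagery period as stress, alcohol cues or neutral. Section V.9, under The Imagery Procedures, states: "The alcohol cue imagery involves reliving a personal experience involving alcohol-related stimuli associated with alcohol use". Hypothesis 2a in Section V.12 concerns alcohol craving induced by stress and by cues, and Section V.12 compares stress and cue exposure with the neutral condition.

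**The concern.** Staff who follow the written rule can accept a cue script with no alcohol in it, and a stress or neutral script that contains drinking. The outcome of interest is alcohol craving, and the neutral session is the reference for both other conditions. A cue script without alcohol cues weakens the provocation that Hypothesis 2a relies on. A neutral script with alcohol cues raises the reference level. A stress script with alcohol cues makes it hard to say whether a drug effect on stress-induced craving concerns stress, cues or both. The planned rater check would reveal none of this.

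**Working it through.** No sample size, effect size or power figure in the documents bears on this point, so the check compares the passages and then reasons about direction.

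**Step 1: cue script, rule against intent.** The rule sets two conditions: the scene includes drug-related stimuli, and it led to later alcohol use. The second ties the scene to drinking, but it does not require an alcohol stimulus within the scene. In the examples, the bar is only the place where others are watched using drugs. The design overview, Table 1 and Section V.9 require alcohol cues. Rule and intent differ.

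**Step 2: comparator scripts.** The stress exclusion names drug-related stimuli and illustrates them with a possession arrest and a police chase. The neutral exclusion names drug cues. Alcohol appears in neither, and the stress paragraph itself expects stressful events to arise in an alcohol context.

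**Step 3: does drug include alcohol?** The documents point both ways.
- For: the cue paragraph treats "going to a bar after a marital conflict, or feeling depressed and calling a drug using buddy" as drug-related situations, although it disallows them because of the negative affect. Section V.9 uses alcohol cue and drug cue for the same imagery within one paragraph. Section V.12 measures alcohol use partly by self-reported drug use.
- Against: the Substance Use Calendar description lists alcohol and other drugs as separate items. Laboratory Assessments uses separate craving scales for cocaine and alcohol. The safeguards in Section V.9 pair alcohol and drug with a slash.

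The protocol gives no definition that settles it.

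**Step 4: can the check detect it?** A drinking scene and a drug scene can receive the same scores for stress and emotion. The check cannot tell them apart.

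**Step 5: direction.** Let Δ be the rise in craving from a true alcohol cue over neutral. Let p be the share of cue scripts that evoke no such rise, and q the share of neutral scripts that evoke it in full. Then

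- cue minus neutral = (1 − p)Δ − qΔ = (1 − p − q)Δ.

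If treatment changes the alcohol-cue response by δ, the between-arm difference in this contrast becomes (1 − p − q)δ. If a share r of stress scripts also carries an alcohol cue and the effects add, the treatment effect on stress-induced craving becomes δ(stress) + rδ. Contamination therefore shrinks the cue contrast and mixes cue effects into the stress contrast. The documents give none of p, q, r, Δ or δ, so the calculation stops at direction.

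**The case against.** The strongest reply is that the protocol uses drug loosely. If a bar visit counts as a drug-related situation, the exclusions on drug cues already cover alcohol and only the examples need tidying. This reading is plausible, and it makes the point one of wording more than of design. It does not remove the point. The broad meaning is never stated, other sections separate the two terms, and even under it buying crack remains an accepted cue for an alcohol-craving outcome.

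Second, each cue scene must have led that participant to drink. This stands. A reader might infer that the cue condition cannot provoke alcohol craving at all; the trigger requirement shows that this goes too far.

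Third, a reader might infer from the exclusion of current psychoactive drug use and of severe other-substance disorders that many participants could not supply a drug scene. The documents do not support this. The second exclusion reaches only severe disorders, apart from opiates. Co-morbid drug use is an exploratory moderator, and cocaine craving and withdrawal are measured. A clean urine screen does not rule out a past scene with drug-using friends, and no proportion is given.

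Fourth, the cited imagery manual may specify alcohol cues. It is not part of the documents, so this cannot be judged, and the protocol text would still be inconsistent.

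**Conclusion.** The point holds as an inconsistency between the script-building rule and the construct under test, with comparator exclusions that can be read to admit alcohol and a check that would miss it. The expected consequence is a diluted cue-versus-neutral contrast and some confounding of stress with cue effects.

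Two stronger conclusions might be drawn, and neither is supported. One is a stated loss of power: the documents give no effect size or variance for this contrast and no share of affected scripts, so any figure would only reflect the inputs chosen. The other is bias between arms: assignment is randomised and staff and participants are blind, so script content should be distributed similarly across the three groups.

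The reach is also limited. Laboratory craving is not among the 8-week primary outcomes in Section V.12, and the study is described as preliminary and mostly descriptive. The conclusion assumes that staff apply the protocol text as written and that the manual does not already correct it. The correction is still worth making, because the laboratory hypotheses rest on what the scripts contain.

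**What to change.** In Section V.3, Imagery Script Development Session:

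1. Define the cue script by alcohol-related stimuli, keep the requirement that the scene led to alcohol use, and replace the drug examples with alcohol examples.
2. Bar both alcohol cues and drug cues from the stress and neutral scripts, by name.
3. Add one item to the existing independent rating form: alcohol cue present or absent. Require present for cue scripts and absent for the other two, with a new script requested otherwise, as the protocol already does for low ratings.
4. Use one term for the condition throughout, in line with the design overview, Table 1 and Section V.9, and carry it into the factor labels in Section V.12.

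The cost is revised wording in the protocol and, if needed, the script manual, plus one extra item for raters who already score every script. No visit, procedure or participant is added.

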Once a subject is deemed eligible, signs consent and completes all intake assessments, s/he will be randomized to 300mg PREG, 500mg PREG, or PLA and exposed to three laboratory sessions as close together as possible of guided imagery of stress, drug cues and neutral-relaxing cues in week 2 (identified as lab DAY 1, DAY 2, and DAY 3). In a session prior to laboratory sessions, subjects will participate in an imagery script development to provide descriptions of recent stressful, drug cue related and neutral relaxing situations to the research assistant. On the day before laboratory session 1 , subjects will participate in a relaxation and imagery training and IV habituation session, followed by three laboratory sessions that include IV blood drawing.

Daily surveys using a Smartphone platform (MetricWire) monitoring will prompt subjects to take study medication, and provide responses on their alcohol use, craving, stress and mood states for the day (see below for detailed description).

Genetic studies:

Ten mL of whole blood will be collected during physical examination to assess eligibility, and thirty-two mL of whole blood will be also collected from patients on the day of the first laboratory session (LAB DAY 1) for the purposes of understanding genetic factors that may affect craving.

Throughout the 8 week study, subjects will self-administer 300mg/day, 500mg/day or PLA/day and study staff will provide weekly medication packs to subjects.

Participants will be seen twice per week at the Yale Stress Center at [name] to receive once/week counseling, provide urine and receive contingency management for treatment attendance. Daily surveys using the smartphone platform (MetricWire) monitoring will prompt subjects to take study medication, and provide responses on their alcohol use, craving, stress and mood states for the day. Smartphone data will be collected daily. Subjects will be prompted at two random times in the morning and afternoon to complete a brief 1-minute survey of questions and a third 5-10 minute survey to be completed at night before bedtime. The surveys are set up with standard automated questions and prompts and subjects will use the smartphone key pad to answer the prompts (via MetricWire).

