F. Describe the provisions for protection of participant privacy

Samples will be marked only by study ID numbers and no other personal identifying information will be sent to the laboratory. Once genetic analysis is conducted the data will be sent back to our laboratory and the genetic data will be stored in computerized research records that will then be analyzed by group analysis.

G. Describe the methods for the security of storage and sharing of materials

Upon enrollment, all study subjects will be assigned a unique study number. The study number—and no personal identifiers—will be used as labels for study records, samples and any other related research documentation. All electronic and digital files will be stored on the secure Yale network, and the PC accessing the network will be password protected and encrypted. All paper files, such as consent forms, will be stored in a locked file cabinet in a locked office and access is limited to members of the study research team.

Genetic and Gene-Expression Measures.

During the physical examination at study entry, 10 ml of whole blood will also be drawn to analyze molecular adaptations.

Thirty-two mL of whole blood will be collected from patients on day 1 of the laboratory sessions, separately from the blood draws during the lab sessions, for the purposes of understanding genetic factors that may influence the way in which the subject behaves/feels.

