Thus, mixed linear models will be used to test the hypotheses for each of the specific aims. In each case, Subjects will be treated as a random effect and Sex, Imagery Condition and Timeperiod will be treated as fixed effects. PROC MIXED in the Statistical Analysis System (SAS, version 9.3) will be used to model the experimental effects. Each of the specific aims and hypotheses are listed below. For the treatment section of the study, Cox Proportional Hazards models will be used to ascertain differences in time to relapse between AUD individuals treated with pregnenolone compared with those treated with placebo. We anticipate that pregnenolone-treated individuals will demonstrate a survival function reflecting an increase in number of days to relapse compared to the placebo group.

Specific Aim #1: *To evaluate the safety/tolerability of 300mg and 500 mg/day of PREG vs PLA in AUD individuals. Hypothesis 1: PREG 300 and 500 mg/day will be found to be safe, well-tolerated and with fewer side effects/adverse events as compared to the PLA group. Statistics to test hypothesis 1 will compare safety and adverse events data using percentages of various side effects and number and type of AE's for the three treatment groups by each week in treatment using PROC MIXED procedures in SAS, but also frequencies of overall AEs compared across the 8-week period.*

Specific Aim #2a: To evaluate PREG dose (PLA, 300 and 500 mg/day) effects on ALLO and on provoked cue- and stress induced craving, HPA responses, anxiety/mood and cognitive flexibility in AUD patients.

Hypothesis 2a: Compared to PLA, PREG will dose dependently increase ALLO levels and also decrease stress and cue-induced alcohol craving, anxiety, normalize HPA axis basal and response levels of Cortisol, ACTH and adrenal sensitivity (Cortisol/ACTH ratio) and improve Stroop cognitive flexibility.

Specific Aim #2b: To assess whether PREG-stimulated ALLO levels mediate its effects on provoked craving, anxiety, mood, HPA axis response and cognitive flexibility in the laboratory component. Hypothesis 2b: Compared to PLA, higher ALLO levels in the PREG dose groups will mediate greater reductions in alcohol craving, anxiety, mood, cognitive flexibility and normalizing of HPA axis measures specified in Hypothesis 2a.

Specific Aim #3a: To determine the efficacy of 8-week PREG doses versus PLA treatment on primary alcohol use outcomes, and secondary outcomes including alcohol craving, anxiety and mood.

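### Training and IV habituation are scheduled on two different days, and the laboratory model lists no session-day term, so any Day-1 difference in reactivity stays in the imagery contrasts as noise

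*Combined protocol and SAP*

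**What the plan says.** Section V.3, General Procedures, under Laboratory Sessions: "On the day before laboratory session 1 , subjects will participate in a relaxation and imagery training and IV habituation session". The later subsection headed Imagery and Relaxation Training and IV Habituation Day has instead: "On LAB DAY 1, subjects will arrive at the lab at 11 AM on the day of the first laboratory session". That subsection continues: "At the end of training, the subject will be given lunch and prepared for the first laboratory session". Table 1 also gives 11 AM on Lab Day 1 for a one-hour training session, with the imagery session set up at 2 PM.

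Genetic and Gene-Expression Measures adds a separate sample: "Thirty-two mL of whole blood will be collected from patients on day 1 of the laboratory sessions". Section V.9 gives the routine load: "During each laboratory session, about 120mL of whole blood will be drawn to measure stress hormone levels".

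On imagery order, the Imagery Script Development Session subsection says: "The order of stress, neutral and drug cue scripts will be assigned randomly, and counterbalanced across subjects". Section V.12, Data Analytic Procedures, repeats this. Neither place mentions treatment arm or sex.

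On the model, Section V.12 names Treatment and Sex as between-subject factors and Imagery Condition and Time Period as within-subject factors. It then says "Subjects will be treated as a random effect and Sex, Imagery Condition and Timeperiod will be treated as fixed effects". No day, order or sequence term is listed. The rule for adding covariates covers demographic, substance-use and psychiatric-history or predictor variables; it does not mention session order.

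**The concern.** The laboratory part is a three-period within-subject comparison: each participant has stress, alcohol-cue and neutral imagery on separate days. In such a design, anything peculiar to the first day attaches to whichever imagery type falls on it.

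Lab Day 1 may well differ from the other two. On the same-day schedule it alone has an 11 AM arrival, an additional catheter placement, relaxation and imagery practice, and lunch before the 2 PM session. On either schedule it alone has the genetic sample. The protocol itself treats catheter insertion as a stressor, and the outcomes are stress hormones, catecholamines, anxiety and craving. With no day term, a Day-1 difference in reactivity goes into the error of the stress-minus-neutral and cue-minus-neutral contrasts that Aim 2a compares between arms. The sex comparisons, also a stated aim, rest on cells half that size.

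**Working it through.** **Inputs from the documents.** Three arms of 30 (3 × 30 = 90); half women, so about 15 per arm-by-sex cell; three imagery types, hence six orders. The sample size has no power calculation behind it to reproduce. The documents give neither a Day-1 effect nor a between-session correlation.

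**Scheduled blood.** Lab Day 1: about 120 + 32 = 152 mL. Days 2 and 3: about 120 mL each.

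**Set-up.** The unit is the SD of the within-subject stress-minus-neutral contrast, and *d* is the Day-1 effect in that unit (assumed: 0.25, 0.5, 1.0). For each participant let *c* = +1 if stress falls on Day 1, −1 if neutral does, and 0 if the alcohol cue does. The contrast then picks up *d* × *c*. Each value of *c* arises in two of the six orders, so *c* has mean 0 and variance 4/6 = 2/3.

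**Bias.** Order is random with respect to arm, so the expected between-arm difference in mean *c* is 0.

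**Chance imbalance.** With 15 participants per order over all 90 and no balancing within arm, the SD of the difference in mean *c* between two groups of size *n* is √[(2/3)(90/89)(2/*n*)].
- *n* = 30: 0.212 (0.21 in 40,000 simulated trials; 95% within 0.40).
- *n* = 15: 0.300 (simulated 0.30; 95% within 0.60).

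Multiply by *d* for the shift in the estimate. In head counts, two arms differ by 5 or more in the number with stress on Day 1 in 22% of trials. This describes the same variation and is not a further loss.

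**Precision without a day term.** The variance per participant becomes 1 + (2/3)*d*², and the standard error of an arm comparison is √[(1 + (2/3)*d*²)(2/30)]. This gives 0.264, 0.279 and 0.333 for *d* = 0.25, 0.5 and 1.0, against √(2/30) = 0.258 with no Day-1 effect.

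**Type I error and power.** Two-sided 0.05, assumed drug effect 0.75 SD, 4,000 simulated trials per entry (simulation error about 0.006 at power 0.80). The day term here is a Day-1 covariate.

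| *d* | Balanced overall, no day term: type I / power | Balanced overall, day term: power | Balanced within arm, no day term: type I / power | Balanced within arm, day term: power |
|---|---|---|---|---|
| 0.25 | 0.054 / 0.80 | 0.80 | 0.050 / 0.82 | 0.81 |
| 0.5 | 0.048 / 0.76 | 0.82 | 0.029 / 0.76 | 0.83 |
| 1.0 | 0.047 / 0.61 | 0.82 | 0.010 / 0.62 | 0.83 |

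Type I error with the day term is about 0.05 throughout. Balancing within arm without the term steadies the estimate but leaves the Day-1 variance in the residual, so the standard error is too large and the test conservative. The day term recovers the power; balancing adds little once it is there.

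**The case against.** A reader might infer that the Day-1 load contaminates the drug-by-imagery contrasts. The documents do not support that: order is random, the expected contribution is zero, and unadjusted type I error stays at its nominal level.

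A reader might also infer that order is deliberately balanced only over the whole sample. That is a reading of silence. No section excludes balance within arm, and detailed procedures are referred to a separate manual. The fixed-effects sentence is likewise incomplete: it leaves out Treatment, which the preceding paragraph names as a factor, so the absence of session day does not prove it would be omitted.

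Other points limit the size. A Day-1 shift that raises baseline and post-imagery values equally cancels from change-from-baseline responses; only a change in reactivity survives. Habituation is meant to reduce first-session stress, and whether same-day training raises or lowers Day-1 reactivity cannot be told from the documents. The time of day of the genetic sample is not stated, so it may follow the imagery session. Section V.12 also calls the study preliminary and mostly descriptive.

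All of this stands, and it makes the point one of precision. It does not remove the contradiction over the training day. Nor does it supply a reason to leave session day out of a three-period analysis, particularly one meant to yield effect sizes for a larger trial.

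**Conclusion.** The point holds as a matter of precision and consistency. The protocol gives two incompatible days for training and habituation, and its laboratory model as written has no term to take up a difference between session days.

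The loss depends on an assumption that the documents cannot settle. It is negligible if the Day-1 effect on reactivity is 0.25 SD of the within-subject contrast, modest at 0.5 SD (power 0.76 against about 0.82 with the term) and substantial at 1.0 SD (0.61 against 0.82). These powers also assume a 0.75 SD drug effect and complete sessions. Chance imbalance matters more in the arm-by-sex cells, where its SD is about 1.4 times that for whole arms (0.30/0.21).

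**What to change.** 1. **Enter session day (1, 2, 3) as a fixed effect in the laboratory mixed model.** This is the essential change. It uses data already collected and costs two degrees of freedom. Where the seven time periods are modelled directly, rather than a per-session change, peak or area under the curve, add session day by time period as well, since the day main effect alone removes only a level shift. That interaction costs 2 × 6 = 12 more.
2. **Optionally, balance the six imagery orders within each treatment arm** (30/6 = 5 per order), and only together with the day term. The cost is one extra column in the randomization list. Within arm-by-sex cells of 15, six orders cannot be equal, but three Latin-square orders can (5 each).
3. **Reconcile General Procedures with the habituation subsection and Table 1,** so that every participant follows one training and habituation schedule. Which schedule is for the investigators to decide; the edit is to wording, plus any change in visit arrangements that follows from their choice.
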